#### **12.6.4.4 Vital Signs, Physical Findings and Other Observations Related to Safety**

##### **12.6.4.4.1 Prior and Concomitant Medication**

Prior medication is defined as any medication that started and ended prior to Screening. Concomitant medication is defined as any medication starting on or after Screening. Medications that started prior to Screening and are ongoing at Screening are considered as concomitant.

All medications will be listed by product using PT and Anatomical Therapeutic and Chemical (ATC) codes (World Health Organization-Drug Dictionary Enhanced [WHO-DDE] Q1 2012). A flag will be presented on the listing indicating whether the medication is prior or concomitant. Prior and concomitant medications will be listed by randomization arm. Concomitant medications will be summarized by randomization arm for the Safety population showing the number and percent of subjects who used the medication at least once by ATC 1st and 2nd levels and preferred drug name.

The data will be presented in the below outputs:

TFL number	Title
TABLES	
15.2.6.19.1	Summary of Concomitant Medication by Anatomical Therapeutic Classes (ATC) 1 and 2 – Safety Population
15.2.6.19.2	Summary of Concomitant Medication by Preferred Drug Name – Safety Population
LISTINGS	
15.3.6.4	Listing of Prior and Concomitant Medication

#### 12.6.4.4.2 Physical Examination

Physical examination data recorded at the Screening visit, Admission (Day -2), Day of discharge (Day 6), Day 30 Visit, Day 60 Visit and Day 90 Visit will be listed by product. Subject's data with abnormal and abnormal clinically significant physical examination findings will be flagged. The number of subjects (%) with normal, abnormal and abnormal clinically significant results will be tabulated by body systems for the Randomized period at Baseline, day of discharge, Day 30 Visit, Day 60 Visit and Day 90 Visit, including shifts in normality from Baseline.

Body weight and waist circumference recorded at Admission (Day -2), Day of discharge from Confinement (Day 6), Day 30 Visit, Day 60 Visit and Day 90 Visit; and body height recorded at the Screening visit will also be listed together with BMI. Descriptive statistics of body weight, waist circumference, body height and BMI (BMI will also be categorized as shown in Section 7.5 “Categorical Variables”), at Admission and Day of discharge will be presented.

The data will be presented in the below outputs:

TFL number	Title
TABLES	
15.2.6.23	Summary of Physical Examination of Body Systems – Safety Population
15.2.6.24	Summary of Weight, Waist Circumference and BMI Results – Safety Population
LISTINGS	
15.3.6.12	Listing of Physical Examination Findings, Shift and Changes from Baseline

#### 12.6.4.4.3 Vital Signs

Systolic and diastolic blood pressure, pulse rate and respiratory rate measured during the study will be listed by study visit, including low/normal/high results.

Descriptive statistics will be presented for supine systolic and supine diastolic blood pressure, pulse rate and respiratory rate at baseline, and on every subsequent day of both the confinement and ambulatory periods by product for each study day. Vital signs data will be summarized together with changes from baseline.

The data will be presented in the below outputs:

TFL number	Title
TABLES	TABLES
15.2.6.20	Summary of Supine Vital Signs – Safety Population
LISTINGS	LISTINGS
15.3.6.9	Listing of Vital Signs Data and Changes from Baseline

#### 12.6.4.4.4 Full Lung Function Data

Lung function parameters assessed during the study include:

- DLCO.
- KCO.
- FEV1.
- FVC.
- VC expressed as L.
- TLC.
- FRV.
- IC.
- Mid expiratory flow (25-75)
- Measurement interpretation (categories: normal, abnormal, abnormal clinically significant)

The above data are collected at Screening, Day 0, Day of discharge from Confinement (Day 6) and Day 90 Visit. At Screening, data are collected prior and post-bronchodilator, also including the brand (trade) name and dose of the bronchodilator. All other spirometry assessments are performed without bronchodilator.

Spirometry predicted values will be standardized to the National Health and Nutrition Examination Survey III predicted set (**Hu and Cassano, 2000**). Spirometry data values and normality evaluation will be listed by randomization arm and study day. Assessments performed after Baseline will be listed together with change from Baseline and shift in normality. Spirometry data from subjects who had significant clinical findings will be highlighted in listings.

Descriptive statistics will be presented for DLCO, KCO, FEV1(L), FEV1 (% pred), FVC(L), FVC(% pred), FEV1/FVC, VC, TLC, FRV, IC, mid expiratory flow (25-75) at Baseline (pre or without bronchodilator), Day of Discharge from Confinement (Day 6), and Day 90 Visit by randomization arm, and overall for the Safety population in the Randomized period. Spirometry data will be summarized together with changes from baseline, and the number and percentage of subjects with normal/abnormal non clinically significant/abnormal clinically significant results. Data with and without bronchodilator at Screening will be summarized together with the spirometry data at Day 0 for the Safety population in the Pre-randomization period.

The data will be presented in the below outputs:

TFL number	Title
FIGURES	
15.1.2.30	Full Lung Function Results Mean and 95% CI – Safety Population
TABLES	
15.2.6.22	Summary of Full Lung Function Results – Safety Population
LISTINGS	

---

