3.2 Secondary Objectives

The secondary objectives of this study are:

- To evaluate self-reported nicotine/tobacco product use including dual-use in an ambulatory setting in smokers switching from mCC to THS 2.2 Menthol as compared to smokers continuing to smoke mCC and to smoking abstinence (SA).
- To determine the reduction of secondary BoExp in a confinement setting and in an ambulatory setting in smokers switching from mCC to THS 2.2 Menthol as compared to smokers continuing to smoke mCC.
- To describe the levels of primary and secondary BoExp over the entire exposure period (confinement and ambulatory periods) in smokers switching from mCC to THS 2.2 Menthol as compared to smokers continuing to smoke mCC and to SA.
- To determine the levels of nicotine over the entire exposure period (confinement and ambulatory periods) in smokers switching from mCC to THS 2.2 Menthol as compared to smokers continuing to smoke mCC and to describe their levels over the entire exposure period.
- To describe the pharmacokinetic profiles of the nicotine and cotinine in a confinement setting in smokers switching from mCC to THS 2.2 Menthol as compared to smokers continuing to smoke mCC.
- To describe the change in CYP1A2 enzymatic activity in smokers switching from mCC to THS 2.2 Menthol as compared to smokers continuing to smoke mCC and to SA.
- To determine the changes in lung functions in smokers switching from mCC to THS 2.2 Menthol as compared to smokers continuing to smoke mCC.

Data and information contained in this document are considered to constitute trade secrets and confidential commercial information, and the legal protections provided to such trade secrets and confidential information are hereby claimed under the provisions of United States law. No part of this document may be publicly disclosed without the written consent of Philip Morris International.

- To monitor the safety profiles during the study.
- To monitor selected risk markers in a confinement and ambulatory setting in smokers switching from mCC to THS 2.2 Menthol as compared to smokers continuing to smoke mCC and to SA.

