  - Nicotine equivalents (NEQ) (expressed in quantity excreted and concentration adjusted for creatinine) in 24-hour urine from Day 1 to Day 5, Day 30 Visit, Day 60 Visit and Day 90 Visit.
  - Nicotine and cotinine in plasma from Day 1 to Day 4, Day 5, Day 30 Visit, Day 60 Visit, and Day 90 Visit.

5. To describe the pharmacokinetic (PK) profiles of nicotine and cotinine in smokers in a confinement setting switching from mCC to THS 2.2 Menthol as compared to smokers continuing to smoke mCC.

Endpoints:

- Peak (highest concentration value along the day) on Day 5.
- Time to peak (actual time when the peak was observed compared to the time of the first cigarette) on Day 5.
- Weighted average concentration over 24 hours on Day 5.

6. To describe the change in Cytochrome P450 1A2 (CYP1A2) enzymatic activity in smokers switching from mCC to THS 2.2 Menthol as compared to smokers continuing to smoke mCC and SA.

Endpoint:

- Molar metabolic ratio of paraxanthine (PX)/caffeine (CAF) in plasma on Day 5 and Day 90 Visit.

7. To determine the changes in lung function in smokers switching from mCC to THS 2.2 Menthol as compared to those continuing to smoke mCC.

Endpoint:

Full lung functions:

- Diffusion capacity for lung CO (DLCO).
- Rate constant for lung CO (KCO).
- Forced expiratory volume in 1 second (FEV1).
- Forced vital capacity (FVC).
- Vital capacity (VC) expressed as L.
- Total lung capacity (TLC).
- Forced residual volume (FRV).
- Inspiratory capacity (IC).
- Mid expiratory flow (25-75)

8. To monitor the safety profiles during the study.

Endpoints:

- AEs, SAEs and device events, including THS 2.2 Menthol malfunction and misuse.
- Respiratory symptoms: cough assessment by visual analogue scale (VAS), Likert scales, and one open question.
- Vital signs.
- Electrocardiogram (ECG).
- Clinical chemistry, hematology, and urine analysis safety panel.
- Physical examination.
- Concomitant medications.

9. To monitor selected risk markers in a confinement and ambulatory setting in smokers switching from mCC to THS 2.2 Menthol as compared to smokers continuing to smoke mCC and to SA.

Endpoints:

- Systolic and diastolic blood pressure on Day 6, Day 30 Visit, Day 60 Visit, and Day 90 Visit.
- High sensitive C-reactive protein (hs-CRP), homocysteine, blood glucose, low density lipoprotein (LDL), high density lipoprotein (HDL), triglycerides (TG), and total cholesterol (TC) in serum on Day 30 Visit, Day 60 Visit, and Day 90 Visit.

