## 12 PLANNED STATISTICAL METHODS

### 12.1 General Considerations

Data analysis will be performed using SAS® Version 9.3.

Data listings will be provided for all data collected as defined in the protocol, ordered by randomization arm and subject, Day, Visit and time point (if applicable), unless otherwise stated. Summary statistics and statistical analysis will only be presented for data where detailed in this SAP. All unscheduled assessments will be included in the listings.

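### Lung-function change is a comparative secondary objective (THS 2.2 Menthol versus continued mCC), but neither document pre-specifies a between-arm estimate for it

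*SAP*

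**What the plan says.** Protocol 3.2 states the objective as "To determine the changes in lung functions in smokers switching from mCC to THS 2.2 Menthol as compared to smokers continuing to smoke mCC". SAP 5.2 repeats it as secondary objective 7, separate from the safety-monitoring objective 8, and lists nine parameters: DLCO, KCO, FEV1, FVC, VC, TLC, FRV, IC and mid expiratory flow.

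The analysis appears only in SAP 12.6.4.4.4, under Safety Evaluation. It says "Descriptive statistics will be presented for DLCO, KCO" and the other parameters, to be given "by randomization arm, and overall for the Safety population in the Randomized period", and "Spirometry data will be summarized together with changes from baseline" and with counts of normal and abnormal results. The outputs are a figure titled "Full Lung Function Results Mean and 95% CI", a table titled "Summary of Full Lung Function Results" and a listing. No model and no difference between arms is named.

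SAP 12.6.2 (Secondary Analyses) has no lung-function subsection, and lung function is not in the risk-marker list of 12.6.2.5. In the protocol, 12.6.3 makes descriptive summary on the FAS the general rule for secondary endpoints, and 12.6.4 confines inference to secondary BoExp and selected risk markers.

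**The concern.** The objective is worded as a comparison, and the planned output does not compare. A reader of the study report will see separate means and intervals for each arm and will have to judge by eye whether the arms differ. Separate per-arm intervals are not an interval for the difference, and whether they overlap is a poor guide to it.

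Any contrast would then be chosen after the results are visible: which parameters, which visit, change score or adjusted value, which analysis set. SAP section 9 records that the study team was accidentally unblinded, which makes it more useful to fix these choices in writing beforehand. Lung-function values are already scheduled on Day 0, Day 6 and Day 91 (Protocol 7.4.11.1), so the comparison needs no new data.

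**Working it through.** **No stated figure to reproduce.** Neither document gives a sample size, power, SD or expected effect for lung function. Among endpoints of biological change, Protocol 12.2 covers only CYP1A2 and 11-DTX-B2.

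**Side-by-side check.** Objectives in less demanding words get more analysis:

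| Endpoint (SAP section) | Verb in the objective | Planned THS versus mCC estimate |
|---|---|---|
| Nicotine and cotinine PK (12.6.2.3) | describe | ratio, or median difference for time to peak, with 95% CI |
| CYP1A2 (12.6.2.4) | describe | ANCOVA ratio with 95% CI |
| Risk markers (12.6.2.5) | monitor | ANCOVA difference or ratio with 95% CI |
| QSU-brief, MCEQ, MNWS (12.6.3.2; exploratory) | describe | ANCOVA difference with 95% CI |
| Smoking topography (12.6.3.3; exploratory) | describe | ANCOVA ratio with 95% CI |
| Lung function (12.6.4.4.4) | determine | none |

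**Illustrative precision of the missing contrast, in SD units.** Inputs: 80 THS and 40 mCC (SAP section 8); 40:40 is the SAP's expected Day 90 per-protocol count for Total NNAL (Table 19). SE = SD × sqrt(1/n1 + 1/n2).

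- 80:40: SE = 0.194 SD; 95% half-width = 1.980 × 0.194 = 0.38 SD; difference detectable with 80% power at two-sided 5% = (1.960 + 0.842) × 0.194 = 0.54 SD.
- 40:40: SE = 0.224 SD; half-width = 1.991 × 0.224 = 0.45 SD; detectable difference = 0.63 SD.
- The planned per-arm intervals have half-widths of about 0.22 SD (n = 80) and 0.32 SD (n = 40).

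**What baseline adjustment adds.** The SAP already plans changes from baseline, so the right comparator is a difference in mean change. Assume equal variances and a baseline-to-follow-up correlation r of 0.8-0.9; neither document gives r. The SD of a change is SD × sqrt(2(1 − r)) and the ANCOVA residual SD is SD × sqrt(1 − r²), so their ratio is sqrt((1 + r)/2).

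- r = 0.8: sqrt(0.90) = 0.949, an SE about 5% smaller.
- r = 0.9: sqrt(0.95) = 0.975, an SE about 3% smaller.

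At 80:40 the half-width for a change score would be 0.383 × 0.632 = 0.24 SD (r = 0.8) or 0.383 × 0.447 = 0.17 SD (r = 0.9). For ANCOVA it would be 0.383 × 0.600 = 0.23 SD or 0.383 × 0.436 = 0.17 SD.

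**Conflicts that affect the definition of the outcome.**

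- SAP 12.6.4.4.4 says that all spirometry after Screening is done without bronchodilator. Protocol 7.4.11.1 and footnote d of SAP Table A1 say that it is done with bronchodilator on Day 0, Day 6 and Day 91.
- FRV is a listed endpoint in SAP 5.2 and 12.6.4.4.4, but the lung-volume paragraph of Protocol 7.4.11.1 records VC, FRC, IC and TLC.

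**The case against.** The strongest reply is that description was the protocol's choice. Protocol 12.6.3 and 12.6.4 leave lung function out of the inferential analysis, so a reader who infers that the SAP dropped a protocol-specified test would be wrong: the mismatch with the objective runs through both documents. Comparative phrasing is also habitual here. Urine mutagenicity is described as compared with mCC and SA and is likewise only summarized (SAP 12.6.3.5). That reply stands in part, but the lung-function objective is to determine rather than describe, and it is secondary rather than exploratory.

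Three stronger readings go too far.

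- One might take "Summary statistics and statistical analysis will only be presented for data where detailed in this SAP" (SAP 12.1) as a bar on any contrast. SAP section 3 and 13.4 allow additional analyses that are documented in the study report, so a contrast is unplanned, not forbidden.
- One might conclude that the trial cannot answer the objective. SAP 12.1.3 sets n, mean and SD as defaults and changes are summarized by arm, so a crude difference with an interval can be computed by hand.
- One might credit baseline adjustment with cutting the SE to 44-60% (sqrt(1 − r²) at the assumed r). That is relative to raw Day 91 means, and the plan already has changes from baseline; against those the gain is about 3-5%.

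**Conclusion.** The point holds in this limited form: a comparative secondary objective has no pre-specified between-arm estimate in either document, while other secondary and several exploratory endpoints do. What would be gained is mainly a contrast fixed in advance, with its visit, covariates and analysis set named; extra precision is small. The 3-5% figure rests on an assumed correlation of 0.8-0.9 with equal variances, and the half-widths are in SD units because no lung-function SD is given. The matter is minor in weight: it touches no primary endpoint and the data are already being collected.

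**What to change.** First reconcile SAP 12.6.4.4.4 with Protocol 7.4.11.1 and SAP Table A1 footnote d on bronchodilator use after Screening, and reconcile the FRV endpoint with the recorded FRC. Until then the Day 0 covariate and some outcomes are undefined.

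Then add to the SAP an ANCOVA of the 12.6.2.5 form (Day 0 value, sex, mCC consumption, arm) for each lung-function parameter at the Day 90 Visit (Day 91). Section 12.6.2.5 models Day 90 only, so a Day 6 analysis is an extension and should be named as one. Report the LS mean difference, THS minus mCC, with its 95% CI, on the FAS (the protocol's default for secondary endpoints) and the PP Set. Label it as estimation without a significance claim, because no lung-function power is stated. Make the amendment before database lock, as SAP section 3 requires, and state its timing relative to the unblinding recorded in section 9.

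If the sponsor wants description only, rewording the objective would also remove the mismatch, but the comparative question would then be given up.

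The cost is a table for each analysis set, using existing code, and more unadjusted secondary intervals: up to 9 parameters × 2 visits × 2 sets = 36.

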**TFL number Title**

15.3.6.11	Listing of Full Lung Function Data and Changes from Baseline
-----------	--

**12.6.4.4.5 Electrocardiogram**

The ECG data will be obtained directly from the 12-lead ECG traces, i.e. not centrally read. These data include the PR, QT, and QTcB intervals; QRS duration; and heart rate; and normality evaluation (normal, abnormal non-clinically significant, clinically significant, together with any PI comments to the abnormality). In addition the QTcF value will be presented.

ECG data values and normality evaluations will be listed by product and study day (Screening, Day 6, Day 30 Visit, Day 60 Visit and Day 90 Visit) together with changes from baseline and shift in normality. ECG data from subjects which had significant clinical findings will be highlighted in listings.

Descriptive statistics will be presented for ECG data at baseline, and Day 6, Day 30 Visit, Day 60 Visit and Day 90 Visit by randomization arm. ECG data will be summarized together with changes from baseline, and the number and percentage of subjects with normal/abnormal/abnormal clinically significant results.

The data will be presented in the below outputs:

---

**TFL number Title****TABLES**

15.2.6.21	Summary of ECG Results – Safety Population
-----------	--

**LISTINGS**

15.3.6.10	Listing of ECG Data and Changes from Baseline
-----------	---

**12.6.4.4.6 Assessment of Cough**

Cough questionnaire is assessed on a daily basis from Day 0 to Day 6 and Day 30 Visit, Day 60 Visit and Day 90 Visit. Questionnaire details are reported in Section 7.3.7 “Cough Assessment”.

The number and percentage of subjects reporting a cough will be summarized by randomization arm and presented for the day prior to the assessment. The responses to the individual items, including the VAS evaluating the level of cough bother and 3 Likert scales measuring the intensity, the frequency of cough and the amount of sputum production will be listed and summarized on each day by randomization arm, for all subjects who filled in the questionnaire. The answers to the open question related to any other important observation will be listed.

The data will be presented in the below outputs:

TFL number	Title
TABLES	
15.2.6.25	Summary of Cough Assessments Over Study – Safety Population
15.2.6.25.1	Summary of Cough Assessments by Study Day – Safety Population
LISTINGS	
15.3.6.23	Listing of Cough Assessment Results

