7.8.3.2 Assessment of Cough

Subjects will be asked to assess the respiratory symptom 'cough' on a VAS, on three Likert scales, and with an open question on a daily basis during the confinement period (from Day 0 to Day 6), and at every visit on Day 30 Visit (Day 31), Day 60 Visit (Day 61) and Day 90 Visit (Day 91). From Day 0 to Day 6 only, assessment of cough must be done prior to start of

Data and information contained in this document are considered to constitute trade secrets and confidential commercial information, and the legal protections provided to such trade secrets and confidential information are hereby claimed under the provisions of United States law. No part of this document may be publicly disclosed without the written consent of Philip Morris International.

product use/smoking and no later than 10:00 AM. On Day 31 and Day 61, and Day 91, assessment of cough will be conducted irrespective of the time of product use but no later than 10:00 AM.

Subjects will be asked if they have experienced a regular need to cough, e.g., whether they have coughed several times in the previous 24 hours prior to assessment. If the answer is 'yes', subjects will be asked to complete a VAS, 3 Likert scales, and to answer the open question.

On the VAS, subjects will assess how bothersome their cough was during the previous 24 hours. The VAS ranges from 'not bothering me at all' to 'extremely bothersome.'

Furthermore, subjects will assess the intensity and frequency of cough and the amount of sputum production during the previous 24 hours on Likert scales.

The intensity of cough will be assessed on a 5-point Likert scale ranging from 1 to 5, with 1 = very mild – 2 = mild – 3 = moderate – 4 = severe – 5 = very severe.

The frequency of cough will be assessed on a 5-point Likert scale ranging from 1 to 5, with 1 = rarely – 2 = sometimes – 3 = fairly often – 4 = often – 5 = almost always.

The amount of sputum production will be assessed on a 4-point Likert scale ranging from 0 to 3, with 0 = no sputum – 1 = a moderate amount of sputum – 2 = a larger amount of sputum – 3 = a very large amount of sputum.

Finally, subjects will be asked to share any other important observations with the staff about their coughing.

7.8.3.3 *Modified Cigarette Evaluation Questionnaire*

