12.6.5 Safety Analysis

In general, all safety data will be listed and tabulated on the safety population by study arm, using the approach described in Section 12.1.3. Safety variables collected during exposure periods will also be reported by product exposure.

Adverse event data will serve as the primary assessment of safety. Other safety variables monitored in this study include: respiratory symptoms (cough assessment VAS and Likert scales); vital signs (systolic and diastolic blood pressure, pulse rate, respiratory rate); electrocardiogram (ECG) data; clinical chemistry, hematology, concomitant medications, and urine analysis safety panel; physical examination.

The number and percentage of subjects with AEs and SAEs will be tabulated by system organ class (SOC) and preferred term (PT). Summaries will also be presented for AEs leading to withdrawal, AEs leading to death, AEs by relatedness to product exposure, AEs by severity, and laboratory AEs. Tabulations will be performed for both the number of subjects experiencing an event and the number of events.

The number and percentage of subjects with clinical findings by sequence for laboratory parameters will be summarized for the safety population. Shift tables showing change from baseline of clinical findings will be provided for: ECGs, physical examinations and laboratory parameters (both shifts in normal ranges and toxicity grades). Descriptive statistics will be summarized by visit and change from baseline for laboratory parameters, ECG, respiratory symptoms, and vital signs.

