### 7.3.7 Cough Assessment

Subjects will be asked to assess the respiratory symptom ‘cough’ on a VAS, on three Likert scales, and with one open ended question on a daily basis during the confinement period (from Day 0 to Day 6), and on the second day of each ambulatory period visit (Day 30 Visit, Day 60 Visit and Day 90 Visit ). From Day 0 to Day 6, assessment of cough is done prior to start of product use/smoking and no later than 10:00 AM. On Day 31, and Day 61 assessment of cough will be conducted irrespective of the start of product use and not later than 10:00 AM. On Day 91 the assessment of cough will be conducted irrespective of the start of product use and not later than 10:00 AM.

Subjects will be asked if they have experienced a regular need to cough, e.g., whether they have coughed several times in the previous 24 hours prior to assessment. If the answer is ‘yes’, subjects will be asked to complete questionnaire.

The VAS will assess how bothersome cough is to the subject ranging from ‘not bothering me at all’ to ‘extremely bothersome’, and this will be given a numeric value between 0 and 100, measured on a 100mm scale.

Subjects will also be asked to assess the intensity and frequency of cough and the amount of sputum production on Likert scales as presented in **Table 8**.

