**Table 8 : Cough Assessment Likert Scales**

Question	Likert Scale
1 The intensity of cough	1 = very mild 2 = mild 3 = moderate 4 = severe 5 = very severe
2 The frequency of cough	1 = rarely 2 = sometimes 3 = fairly often 4 = often 5 = almost always
3 The amount of sputum production	0 = no sputum 1 = a moderate amount of sputum; 2 = a larger amount of sputum; 3 = a very large amount of sputum.

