**Table 27: List of Laboratory Safety Parameters**

Hematology	Clinical chemistry	Urine analysis
Hematocrit	Albumin	pH
Hemoglobin	Total protein	Bilirubin
Mean corpuscular hemoglobin	Alkaline phosphatase	Glucose
Mean corpuscular hemoglobin concentration	Alanine aminotransferase	Nitrite
Mean corpuscular volume	Aspartate aminotransferase	Red blood cell traces
Platelet count	Blood urea nitrogen	Protein
Red blood cell count	Creatinine	Specific gravity
WBC count Differential	Gamma-glutamyltransferase	
WBC count:	Fasting glucose	
• Neutrophils	Lactate dehydrogenase	
• Basophils	Potassium	
• Eosinophils	Sodium Total	
• Lymphocytes	bilirubin Direct	
• Monocytes	bilirubin	
	Total cholesterol	
	Triglycerides	

Any clinical safety laboratory test result that is outside of the normal reference range will be reviewed by the principal investigator (PI) and assessed for clinical relevance. If the PI considers the abnormal result to be of clinical relevance, then it must be recorded as a concomitant disease at Screening, or if not present at Screening, as an AE during the study. If the condition worsens from screening to after product-use it will be recorded as an AE.

The grading scheme used in the Common Terminology Criteria for Adverse Events and Common Toxicity Criteria [CTCAE] version 4.03) will be used by the PI to assess abnormal laboratory values. These CTCAE grades will be derived programmatically in the creation of the datasets.

Laboratory data will be summarized and listed at Screening and Day 0 for the Pre-Randomization period; and at Baseline, Day of Discharge (Day 6), Day 30 Visit, Day 60 Visit and Day 90 Visit for the Randomized period data together with changes from Baseline. The number and percentage of subjects with normal results, high/low results and abnormal clinical significant result (as defined by PI comment), and CTCAE toxicity grading will be tabulated for laboratory parameters, together with shift in normality (Normal, Abnormal NCS, Abnromal CS) and in CTCAE toxicity grading from Baseline.

Listings for the clinical laboratory data will include the following information: change from Baseline, normal/ high/low (with respect to the reference range), abnormal clinically significant (as defined by the PI comments) and shift from Baseline, the PI comments, the CTCAE grade and the shift in CTCAE grade. Only CTCAE grades greater than zero will be presented.

The data will be presented in the below outputs:

TFL number	Title
TABLES	

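### The SAP drops the protocol's change from baseline for cough; it should be restored in a form that keeps subjects whose cough starts or stops (low severity, descriptive only)

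*SAP*

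**What the plan says.** **Who answers the items.** Subjects are first asked whether they had a regular need to cough in the previous 24 hours. After a yes, Protocol 7.8.3.2 says "subjects will be asked to complete a VAS, 3 Likert scales, and to answer the open question", and SAP 7.3.7 says "subjects will be asked to complete questionnaire". Neither document gives a value to a subject who answers no. The intensity scale in SAP Table 8 runs "1 = very mild 2 = mild 3 = moderate 4 = severe 5 = very severe", and the frequency scale starts at 'rarely'. Neither has a level for no cough. The sputum scale does start at zero, but it is put only to subjects who said yes.

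**What is summarised.** SAP 12.6.4.4.6 plans the number and percentage reporting a cough, by arm. The VAS and Likert items "will be listed and summarized on each day by randomization arm, for all subjects who filled in the questionnaire".

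**Baseline comparison.** Protocol 12.6.5 says: "Descriptive statistics will be summarized by visit and change from baseline for laboratory parameters, ECG, respiratory symptoms, and vital signs". The same section identifies respiratory symptoms as the cough VAS and Likert scales. The SAP carries the plan forward for three of the four items:

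- laboratory data (12.6.4.3): "for the Randomized period data together with changes from Baseline"
- vital signs (12.6.4.4.3): "Vital signs data will be summarized together with changes from baseline"
- ECG (12.6.4.4.5): "ECG data will be summarized together with changes from baseline"

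SAP 12.6.4.4.6 has no such statement for cough, in its text or its output titles.

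**The concern.** Cough by VAS and Likert scales is a named secondary safety endpoint (SAP 5.2). Protocol 7.8.3 does not require symptoms reported on the questionnaires to be recorded as adverse events as well, on the ground that the questionnaires and VAS will be analysed. That reasoning depends on the analysis being informative. For an inhaled product, the natural question is whether subjects cough more or less than before they switched, and the protocol planned a comparison for it.

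The SAP does not merely leave the detail open. SAP 12.1 states that summary statistics will be presented only where the SAP details them, so on its wording the change from baseline would not be produced.

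The filter question raises a second matter. Simply adding a numeric change would omit exactly the subjects whose cough began or resolved. It also means that each daily severity row describes a subset defined after randomisation, so a percentage in that row, taken alone, is not a statement about the arm.

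**Working it through.** The documents give no cough rate or score, so there is no plan figure to reproduce. The rates below are assumed. The arm size of 80 is the planned THS 2.2 Menthol arm, and everyone is taken to have answered the cough question.

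**Step 1: what a numeric change would cover.** Assume 24 of 80 cough at baseline, 8 of them resolve and 16 others start.

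- Coughing at both times: 24 − 8 = 16, or 16/80 = 20% of the arm
- Started or stopped: 16 + 8 = 24, with no numeric change
- Never coughing: 80 − 24 − 16 = 40
- Check: 16 + 24 + 40 = 80

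A shift table with a *no regular cough* category places all 80.

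**Step 2: whether the planned daily tables already show this.** They would give the two margins: 24 of 80 at baseline and 24 − 8 + 16 = 32 of 80 later. If r baseline coughers resolve, the number who start is 32 − (24 − r) = 8 + r. Since r can be anything from 0 to 24, the margins allow from 8 to 32 new coughers. The daily tables therefore cannot separate incident from persistent cough.

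**Step 3: the daily severity percentages.** Start with 24 coughers, 6 of them severe: 6/24 = 25% of coughers and 6/80 = 7.5% of the arm. Now let 16 more start to cough and none resolve, so that cough goes from 24/80 = 30% to 40/80 = 50%.

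| Severe among the 16 new | Severe, of coughers | Severe, of arm |
|---|---|---|
| 0 | 6/40 = 15% | 6/80 = 7.5% |
| 4 | 10/40 = 25% | 10/80 = 12.5% |
| 8 | 14/40 = 35% | 14/80 = 17.5% |

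In the middle row the coughers-only percentage does not move while severe cough in the arm rises from 6 subjects to 10. In the last row it moves in the right direction.

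**Step 4: the VAS.** Take 30% coughing at a mean of 40, then a further 20% at mean m. The mean among coughers is (0.30 × 40 + 0.20 × m) / 0.50. For m = 10, 25, 40 and 60 it is 28, 34, 40 and 48.

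The opposite movement is also possible. Take 10 coughers at VAS 20 and 10 at VAS 60, with a mean of 40. If the milder ten stop, the mean among coughers rises to 60. With non-coughers set to 0, the mean over 80 subjects falls from 800/80 = 10 to 600/80 = 7.5.

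**Step 5: what the plan already recovers.** SAP 12.6.4.4.6 gives the incidence, and SAP 12.1.3 requires counts with percentages for categorical data. In the middle row of step 3 the planned output would show 6 becoming 10, and 25% × 50% = 12.5% recovers the arm figure. The Likert part of the problem is thus mostly one of presentation. Step 2 has no such remedy in the planned output.

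**The case against.** Incidence plus severity among those affected is a normal display for a questionnaire with a filter question. The SAP plans no test or model for cough and nowhere proposes that the severity rows be read alone. Every item is shown from Day 0 onward, so baseline and later distributions appear together. MNWS item 12 rates coughing on a 0 to 4 scale with no filter question, in all arms and on a similar schedule. Adverse events remain the primary safety assessment (Protocol 12.6.5), are collected mainly by interview, and may be triggered by questionnaire answers at the investigator's discretion (Protocol 7.8.3 and 8.2.1). Finally, a *no regular cough* row mixes no cough with occasional cough, so it does not sit cleanly below 'rarely'.

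Most of this stands, and it is why the severity is low. Three things remain. Side-by-side daily distributions do not give within-subject change (step 2). MNWS item 12 is outside the MNWS total score, and SAP 12.6.3.2.4 only lists individual answers. The mixing is real, but it concerns how the category is displayed and is no reason to leave those subjects out.

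A reader might infer more, and the documents do not support it:

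- **That the cough tables are invalid or conceal cough.** The planned incidence and counts prevent that.
- **That silence in SAP section 9 breaches the protocol.** Protocol 12.1 sends changes in statistical methods to the Clinical Study Report, so absence from section 9 is at most untidy.
- **That the protocol requires a shift table for cough.** Protocol 12.6.5 names shift tables only for ECG, physical examination and laboratory parameters.
- **That output titles prove intent.** The ECG listing title mentions changes from baseline and the cough listing title does not, but the ECG and vital-signs table titles do not mention them either.

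**Conclusion.** The point holds at low severity. A change-from-baseline summary that the protocol plans for cough is missing from the SAP, while the three sister items keep theirs, and under SAP 12.1 it would not be produced. The detailed table shells are not available here. If they add it, only the form of the comparison remains at issue.

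The coughers-only denominator is a smaller matter, largely offset by what is already planned. Its main relevance is that it rules out a plain numeric change as the way to restore the comparison.

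The conclusion about coverage follows from the filter question alone. The sizes shown (16 of 80 with a numeric change, 25% unchanged while severe cases go from 6 to 10) depend on assumed rates and would differ in the data. No primary endpoint, success criterion or hypothesis test is affected.

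**What to change.** In SAP 12.6.4.4.6:

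1. Add, for each Likert item, a baseline-to-visit shift table by arm that includes *no regular cough*. Show it as a separate category, not as an ordered level below 'rarely' or 'very mild'.
2. Give the daily Likert percentages over all Safety-population subjects who answered the cough question at that assessment, with the same separate category.
3. Keep the VAS summary among coughers and label it so, with n/N. If no VAS change from baseline is shown, record that departure in the Clinical Study Report, as Protocol 12.1 provides.

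The cost is SAP wording and slightly larger tables, with no new data. The yes/no answer is collected in all arms. The Day 1 assessment, made before product use (before 10:00 AM in the SA arm), meets the baseline definition in SAP Table 26. The drawback is that *no regular cough* combines no cough with occasional cough, which a footnote should state. Merely noting the omission in section 9 would change no result and is the weaker option.
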